10.2.3 Causality

The investigator must determine the relationship between the administration of the IP and the occurrence of an AE/SAE as Not Suspected or Suspected as defined below:

Not suspected: a causal relationship of the adverse event to IP administration is **unlikely or remote**, or other medications, therapeutic interventions, or underlying conditions provide a sufficient explanation for the observed event.

Suspected: there is a **reasonable possibility** that the administration of IP caused the adverse event. ‘Reasonable possibility’ means there is evidence to suggest a causal relationship between the IP and the adverse event.

Causality should be assessed and provided for every AE/SAE based on currently available information. Causality is to be reassessed and provided as additional information becomes available.

If an event is assessed as suspected of being related to a comparator, ancillary or additional IP that has not been manufactured or provided by Celgene, please provide the name of the manufacturer when reporting the event.

10.2.4 Duration

For both AEs and SAEs, the investigator will provide a record of the start and stop dates of the event.

10.2.5 Action Taken

The investigator will report the action taken with IP as a result of an AE or SAE, as applicable (eg, discontinuation, interruption, or dose reduction of IP, as appropriate) and report if concomitant and/or additional treatments were given for the event.

10.2.6 Outcome

The investigator will report the outcome of the event for both AEs and SAEs.

All SAEs that have not resolved upon discontinuation of the subject’s participation in the study must be followed until recovered (returned to baseline unless the subject experiences progression of MDS or any other malignancy), recovered with sequelae, or death (due to the SAE).

10.3 Abnormal Laboratory Values

An abnormal laboratory value is considered to be an AE if the abnormality:

- results in discontinuation from the study;
- requires treatment, modification/ interruption of IP dose, or any other therapeutic intervention; or

- is judged to be of significant clinical importance, eg, one that indicates a new disease process and/or organ toxicity, or is an exacerbation or worsening of an existing condition.

Regardless of severity grade, only laboratory abnormalities that fulfill a seriousness criterion need to be documented as a serious adverse event.

If a laboratory abnormality is one component of a diagnosis or syndrome, then only the diagnosis or syndrome should be recorded on the AE page/screen of the eCRF. If the abnormality was not a part of a diagnosis or syndrome, then the laboratory abnormality should be recorded as the AE. If possible, the laboratory abnormality should be recorded as a medical term and not simply as an abnormal laboratory result (eg, record thrombocytopenia rather than decreased platelets).

10.4 Pregnancy

All pregnancies or suspected pregnancies occurring in either a female subject of childbearing potential or female partner of a male subject are immediately reportable events. For adequate measures of contraception please refer to [Section 4.2](#).

10.4.1 Females of Childbearing Potential

Pregnancies and suspected pregnancies (including elevated β -hCG or positive pregnancy test in a female subject of childbearing potential regardless of disease state) occurring while the subject is on IP, or within 12 weeks of the subject's last dose of IP are considered immediately reportable events. Investigational product is to be discontinued immediately and if applicable the subject instructed to return any unused portion of the IP to the investigator. The pregnancy, suspected pregnancy, or positive pregnancy test must be reported to Celgene Drug Safety immediately by email, phone or facsimile, or other appropriate method, using the Pregnancy Initial Report Form, or approved equivalent form.

The female subject may be referred to an obstetrician-gynecologist or another appropriate healthcare professional for further evaluation.

The investigator will follow the female subject until completion of the pregnancy, and must notify Celgene Drug Safety immediately about the outcome of the pregnancy (normal or abnormal outcome) using the Pregnancy Follow-up Report Form, or approved equivalent form.

If the outcome of the pregnancy was abnormal (eg, spontaneous abortion), the investigator should report the abnormal outcome as an AE. If the abnormal outcome meets any of the serious criteria, it must be reported as an SAE to Celgene Drug Safety by facsimile, or other appropriate method, within 24 hours of the investigator's knowledge of the event using the SAE Report Form, or approved equivalent form.

All neonatal deaths that occur within 28 days of birth should be reported, without regard to causality, as SAEs. In addition, any infant death after 28 days that the investigator suspects is related to the in utero exposure to the IP should also be reported to Celgene Drug Safety by facsimile, or other appropriate method, within 24 hours of the investigator's knowledge of the event using the SAE Report Form, or approved equivalent form.

10.4.2 Male Subjects

If a female partner of a male subject taking IP becomes pregnant, the male subject taking IP should notify the investigator, and the pregnant female partner should be advised to call their healthcare provider immediately.

10.5 Other Malignancies/Pre-malignancies

Events of new malignancy, pre-malignant lesions (excluding benign tumors or benign neoplasia) are to be reported to Celgene Drug Safety within 24 hours of the investigator's knowledge of the event by facsimile, or other appropriate method, using the SAE Report Form, or approved equivalent form. All SAE criteria (eg, hospitalization) should be marked if applicable, and all events must be marked as an "Important Medical Event" even if no other serious criteria apply; these events must also be documented in the appropriate page(s) of the CRF and subject's source documents. Documentation related to the diagnosis of malignancy must be provided at the time of reporting as a serious adverse event (eg, any confirmatory histology or cytology results, X-rays, computed tomography [CT] scans, etc.).

Malignancies or cancerous tumors are lesions capable of invading into adjacent tissues, and may be capable of spreading to distant tissues. A benign tumor has none of those properties.

Malignancy or cancer is characterized by anaplasia, invasiveness, and metastasis. For the Myelodysplastic Syndrome (MDS) studies, these also include progression to high/very high risk of MDS (per IPSS-R; [Greenberg, 2012](#)); myeloproliferation (eg, clinically significant increases in blasts), progression to AML, etc.

Premalignant or precancerous lesions refer to a state of disordered morphology of cells that is associated with an increased risk of cancer. If left untreated, these conditions may lead to cancer. Such conditions are usually either dysplasia or benign neoplasia (and the dividing line between those is sometimes blurry). Sometimes the term "precancer" is used to describe carcinoma in situ, which is a noninvasive cancer that has not progressed to an aggressive, invasive stage. Not all carcinoma in situ will progress to invasive disease.

Premalignant lesions are morphologically atypical tissue which appears abnormal under microscopic examination, and in which cancer is more likely to occur than in its apparently normal counterpart.

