6.1.19 Monitoring for Progression to AML and Other Malignancies/Pre-malignancies

Progression to AML as per WHO classification ([Arber, 2016](#)) will be monitored and will be included as part of the safety assessment throughout the course of the study. Progression to AML should be monitored from time of signing of informed consent through 5 years after the first dose of IP, or 3 years from the last dose (whichever occurs later), or until death, lost to follow-up or withdrawal of consent from the study. For that purpose, subjects will be followed post treatment every 12 weeks for 3 years from the date of last dose of IP and every 6 months thereafter, if applicable.

The occurrence of a new malignancy or pre-malignant lesion will be monitored as an event of interest and should be included as part of the assessment of AEs throughout the course of the study (please refer to [Section 10.5](#) for details). Investigators are to report the development of any new

malignancy or pre-malignant lesion as a serious adverse event (SAE), regardless of causal relationship to IP (luspatercept or epoetin alfa), occurring at any time for the duration of the study, from the time of signing the ICF for up to and including long-term follow-up (ie, 5 years from first dose of IP, or 3 years from last dose [whichever occurs later]), or until death, lost to follow-up, or withdrawal of consent for further data collection.

Documentation supporting the diagnosis of progression to AML and other malignancies/pre-malignancies (eg, confirmatory histology or cytology results, etc.) may be requested. Appropriate information related diagnosis of AML and other malignancies/pre-malignancies should be captured on the eCRF and in the subject's source documents.

Refer to [Section 10.5](#) and [Section 10.6](#) for more information regarding reporting requirements.

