6.3.2 Long-term Follow-up

Transfusion data collection will continue until 8 weeks from the date of last dose of IP or from the date of the EOT Visit (whichever is later) ([Section 6.4.1](#)). Subjects should also be followed via telephone contact by the site to verify if transfusions were given outside of the investigative site.

Antidrug antibodies sample(s) may be required in the Post-treatment Follow-up Period for subjects assigned to the luspatercept arm, who terminate the Treatment Period with less than 1 year of ADA monitoring if a subject is ADA positive at the time of treatment discontinuation ([Section 6.6](#)).

An additional pregnancy test is to be performed 12 weeks (± 7 days) from the date of last dose of IP for FCBP ([Section 6.1.14](#)).

All subjects discontinued from protocol-prescribed therapy for any reason should be followed for the below events/therapies for 5 years after the first dose of IP, or 3 years from the last dose (whichever occurs later), or until death, lost to follow-up or withdrawal of consent from the study.

- Progression to AML and other malignancies/pre-malignancies (please refer to [Section 6.1.19](#) and [Section 10.5](#) for details)
- Survival (date and cause of death)
- and subsequent MDS therapies

Subjects may be followed via telephone contact by the site for collection of the above data every 12 weeks for the first 3 years from the date of last dose of IP and every 6 months thereafter (if applicable) until 5 years after the first dose of IP, or 3 years from the last dose (whichever occurs later), or until death, lost to follow-up or withdrawal of consent from the study. Refer to [Table 3](#).

Data regarding subsequent MDS therapies, determination of AML progression and other malignancies/pre-malignancies, and date and cause of death will be recorded in the eCRF. The investigator must make every effort to obtain information regarding the subject's survival status before determining the subject is lost to follow-up. If the subject is discontinued from Long-term Follow-up, the reason for discontinuation should be recorded on the End of Study eCRF.

Long-term follow-up may be conducted by record review (including public records if allowed by local regulations) and/or telephone contact with the subject, family, or the subject's treating physician.

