In circumstances where the next dose of IP is due to be scheduled prior to cytomorphology/cytogenetics results being available, dosing should not be delayed for this reason contingent that the investigator has confirmed absence of signs of disease progression based on review of peripheral blood parameters. However, the investigator must complete assessment of cytomorphology/cytogenetics results within 4 weeks of the MDS Disease Assessment Visit at the

latest (ie, Day 169, Day 337, Day 505, etc. for the MDS disease assessments every 24 weeks thereafter) to continue dosing beyond these 4 weeks.

For subjects to continue open-label treatment with IP, MDS disease assessments will be repeated at the 48-Week MDS Disease Assessment Visit and every 24 weeks thereafter (ie, Day 337, Day 505 etc.; a \pm 14-day time window to allowed for sample collection) to confirm continued clinical benefit and absence of disease progression as per above criteria.

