^c If dose delay is > 12 consecutive weeks, treatment should be discontinued

^d Predose Hgb value not being influenced by RBC transfusion (ie, Hgb result > 14 days after last RBC transfusion or within 3 days from next RBC transfusion); Hgb should be rechecked weekly during dose delay.

^e Upper limit of normal $> 10,000$ total WBC/ μ L or as defined by institutional standards.

^f Peripheral blood smear should be prepared for central pathology lab assessment.

^g At the investigator's discretion, bone marrow samples may also be collected and analyzed centrally to assess MDS disease status (eg, cytomorphology) prior to making decision regarding treatment discontinuation. The central laboratory must also confirm < 5% bone marrow blasts prior to resumption of treatment.

^h The investigator may contact the Medical Monitor prior to making decision regarding treatment discontinuation.

ⁱ Thrombocytopenia, leukopenia, and neutropenia toxicity grades as defined by CTCAE criteria.

^k Every attempt should be taken to assess the blasts count in peripheral blood prior to dosing, however, in circumstances where results are not readily available at the time of planned dosing, the investigator may proceed with dosing provided there are no signs of clinical progression. In this case, results must be evaluated as soon as they become available (but no later than 3 days post dosing). If presence of $\geq 1\%$ blasts in peripheral blood is observed, actions described in table above must be followed immediately.

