9.3 Sample Size and Power Considerations

A total sample size of approximately 350 subjects (175 in the experimental arm [luspatercept (ACE-536)], 175 in the control arm [epoetin alfa]) will have 90% power to detect the difference between a RBC-TI (for 12 weeks associated with a concurrent hemoglobin increase) response rate of 36% in the experimental arm (luspatercept [ACE-536]) and a response rate of 20% in the control arm (epoetin alfa), with the first interim analysis on futility only when about 105 subjects have completed 24 weeks of treatment, or discontinued before reaching 24 weeks of treatment (30% information for primary endpoint). The Lan-DeMets (O'Brien-Fleming) spending function will

³ Instrument-dependent.

be used as the futility boundary. The sample size calculation is based on one-sided alpha of 0.025, test statistics on odds ratio of proportions using the EAST[®] Version 6.4 software system.

A second interim analysis to test the superiority of the luspatercept arm does not alter the above sample size calculation. The study power remains at 90% for the final analysis with 350 subjects and the Lan-DeMets spending function of the O'Brien-Fleming type will be used to control the overall one-sided Type I error rate at 0.025.

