Time to HI-E will be summarized only for subjects who achieve HI-E response. It is defined as time from Week 1 to first onset of achieving HI-E. It will be summarized only for subjects who achieve HI-E within the first 24 weeks from Week 1.

RBC-TI for ≥ 12 weeks (84 days) is defined as the proportion of subjects achieving RBC-TI for ≥ 84 days during any consecutive 84-day period from Week 1 through Week 24.

Duration of RBC-TI ≥ 12 weeks (84 days) is defined as the longest RBC-TI period for subjects who achieve RBC-TI ≥ 12 weeks from Week 1 through Week 24. Subjects who maintain RBC-TI through the end of the Treatment Period or at the time of analysis will be censored at the date of treatment discontinuation, date of analysis or death, whichever occurs first.

Time to RBC-TI ≥ 12 weeks (84 days) will be summarized only for subjects who achieve RBC-TI ≥ 84 days from Week 1 through Week 24. It is defined as the time between Week 1 and the date onset of TI is first observed (ie, Day 1 of 84 days without any RBC transfusions).

Time to first RBC transfusion is defined as time from Week 1 to first RBC transfusion on treatment. Subjects who maintain RBC-TI through the end of the Treatment Period or time of analysis will be censored at the date of treatment discontinuation/time of analysis or death, whichever occurs first.

RBC transfusion burden on treatment is defined as total number of pRBC units transfused within the first 24 weeks of treatment since Week 1.

RBC-TI for ≥ 56 days (8 weeks) is defined as the proportion of subjects achieving RBC-TI for ≥ 56 days during any consecutive 56-day period from Week 1 through Week 24.

RBC-TI for a consecutive 24-week period is defined as the proportion of subjects achieving RBC-TI for ≥ 168 days during any consecutive 168-day period from Week 1 through Week 48.

Progression to AML: time to AML progression is defined as the time between randomization and first diagnosis of AML as per WHO classification of $\geq 20\%$ blasts in peripheral blood or bone

marrow. Subjects with diagnosis of AML will be considered to have had an event. Subjects who have not progressed to AML at the time of analysis will be censored at the last assessment date which does not indicate progression to AML.

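### No blood count or marrow is scheduled after end of treatment, so the arm that stays on drug longer is expected to show more and earlier progression to higher-risk MDS at equal true rates

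*Combined protocol and SAP*

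**What the plan says.** **The event.** Section 10.5 extends malignancy reporting to changes in MDS risk class ("these also include progression to high/very high risk of MDS"), clinically significant blast increases and AML. Section 6.1.19 requires malignancies to be reported when "occurring at any time for the duration of the study", including long-term follow-up.

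**Surveillance on drug.** Under Section 6.4.2, "MDS disease assessments will be repeated at the 48-Week MDS Disease Assessment Visit and every 24 weeks thereafter", after the Day 169 assessment; these visits include central marrow and cytogenetics. Hematology is drawn at the 3-weekly visits in both arms (Table 3). The Table 5 footnote for luspatercept adds "Every attempt should be taken to assess the blasts count in peripheral blood prior to dosing", and Table 7 makes the blast and white-cell checks mandatory at the 3-weekly visits for epoetin alfa.

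**Surveillance off drug.** Section 6.2.2 allows an EOT marrow only if the previous one was more than 90 days earlier. Table 3 schedules no hematology or marrow at the 42-Day or Long-term Follow-up visits. Section 6.3.2 says "Subjects may be followed via telephone contact by the site for collection of the above data every 12 weeks" for 3 years after the last dose, then every 6 months. It also permits record review and contact with the treating physician.

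**Who stays on drug.** Section 6.4.2 requires, at Day 169 and every 24 weeks, a reduction of at least 2 units per 8 weeks and no disease progression.

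**Analysis.** In Section 9.7.2, "time to AML progression is defined as the time between randomization and first diagnosis of AML", with censoring at the last assessment not indicating AML; the kind of assessment is not defined. Table 2 adds number and percentage. Section 9.8 sets out no split by treatment status.

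**The concern.** How hard a subject is looked at depends on being on drug, and being on drug depends on response. If one arm responds better, as the design assumes, its subjects have 24-weekly marrows and 3-weekly counts for longer. A class change that only marrow and cytogenetics can reveal is then more likely to be found, and found sooner, in that arm even when the true rates are the same.

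What is at stake is the reading of long-term safety. Section 1.4.1.1.1 cites hematologic malignancies in juvenile rats and points to the Section 6.3.2 follow-up as a safeguard. The DMC reviews AML progression (Section 9.10.4), and progression to high-risk MDS or AML may go to health authorities as expedited reports on request (Section 10.7). An imbalance produced by surveillance would count against the longer-treated arm, and within an arm the rate would appear to fall once drug stops.

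**Working it through.** **1. The plan's own figures.** The documents give no figure for progression. The only related number is the design effect in Section 9.3: "36% in the experimental arm (luspatercept [ACE-536]) and a response rate of 20% in the control arm (epoetin alfa". It matters here only because it makes luspatercept the expected better-responding, longer-treated arm. It does reproduce on the stated basis ("The sample size calculation is based on one-sided alpha of 0.025, test statistics on odds ratio of proportions"): OR = (0.36/0.64)/(0.20/0.80) = 2.25; n per arm = (1.960 + 1.282)² × (1/0.2304 + 1/0.16)/(ln 2.25)² = 10.51 × 10.59/0.658 ≈ 170, or 340 in total against the planned 350. The present point does not depend on that N.

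**2. What the event needs.** Appendix C scores cytogenetics, marrow blasts, hemoglobin, platelets and neutrophils. A telephone call cannot generate these; it can only relay tests done for other reasons.

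**3. Simulation under equal true rates.** 600,000 subjects per arm, identical hazards and identical testing triggers in both arms.

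- Taken from the documents: 24-weekly marrow and 3-weekly counts on drug; EOT marrow if the last was more than 90 days earlier; 12-weekly contacts off drug.
- Assumed: lower-risk to higher-risk MDS 0.03–0.10 per year; higher-risk MDS to AML 0.2–0.4 per year. Appendix C's times to 25% AML evolution anchor these through ln(4/3)/t: 0.2877/10.8 = 0.027 (Low), 0.2877/3.2 = 0.090 (Intermediate), 0.2877/1.4 = 0.21 (High), 0.2877/0.7 = 0.41 (Very High).
- Also assumed: mean time on drug, off-drug marrow frequency, and a mean 2-month lag before an off-drug AML is reported at the next contact.

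Ratio of detected higher-risk MDS or AML, longer-treated arm over the other, at 2 years:

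| Off-drug marrows | 1.5 vs 1.0 years on drug | 2.1 vs 0.8 years on drug |
|---|---|---|
| none | 1.14–1.19 | 1.34–1.44 |
| one every 2 years | 1.07–1.10 | 1.16–1.20 |
| one a year | 1.05–1.07 | 1.10–1.11 |
| two a year | 1.01–1.03 | 1.04–1.06 |

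One run in the top right cell gave 5.8% against 4.3% detected. At 5 years with no off-drug marrows the ratios are 1.06–1.12 and 1.14–1.30. With off-drug marrows and 1.5 vs 1.0 years on drug they are 1.00–1.02.

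**4. AML alone.** The ratio is 1.02–1.11 at 2 years and 0.99–1.03 at 5 years. With about 1.4% of 600,000 (8,400) events per arm, the simulation error of a ratio is about √(2/8,400) = 0.015, so the lower end of the 2-year range is hardly distinguishable from 1.

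**5. Check of the mechanism.** With one schedule for everyone regardless of drug, the combined ratio is 1.00 at 2 and 5 years. With equal time on drug (1.16 years in both arms) it is 0.99–1.01. Both unequal schedules and unequal time on drug are needed.

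**6. Not modelled.** Follow-up runs to the later of 5 years from first dose or 3 years from last dose, so it lengthens for anyone treated beyond 5 − 3 = 2 years, which raises raw counts in the longer-treated arm. Table 5 also has a cytopenia-triggered marrow that Table 7 lacks; the simulation leaves this out.

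**The case against.** The case on the other side has several parts.

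- **A reader might infer that follow-up is by telephone only.** It is not. Section 6.3.2 permits telephone contact and also names record review and the treating physician. Section 6.1.19 allows diagnostic documents to be requested, and Section 10.5 requires them when a malignancy is reported. What stands is that no count or marrow is scheduled after EOT.
- **A reader might infer that the AML endpoint is materially biased.** AML is the only progression endpoint defined in Table 2 and Section 9.7.2. Overt AML tends to declare itself clinically, and on these assumptions there is almost no excess by 5 years.
- **A reader might infer a large, certain bias.** A simple coverage calculation reaches 1.42. It assumes 70% of one arm continuing for 2.0 further years against 45% of the other for 1.0, with detection of 95% on drug and 20% off: covered years are 24/52 + 0.7 × 2.0 = 1.86 and 24/52 + 0.45 × 1.0 = 0.91, and (1.86 × 0.95 + 3.14 × 0.20)/(0.91 × 0.95 + 4.09 × 0.20) = 2.395/1.683 = 1.42. With the same further years in both arms (1.0 to 2.0) and the other assumptions varied (60–70% continuing, 20–40% off-drug detection), the formula gives 1.03–1.19. It also treats an off-drug miss as permanent, although later tests can find it. The documents fix none of these inputs.
- **A reader might infer that a planned test is invalid.** No between-arm test of IPSS-R class progression is planned. It is a reporting category, Section 9.8 is descriptive, and full detail is left to SAP text that was not in the material reviewed and may contain a rule.

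These limit the point without removing it. Off-drug marrow practice is neither specified nor systematically captured, so the sponsor could not show afterwards that the distortion was small.

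**Conclusion.** The point holds for progression to high or very high IPSS-R risk, as an expectation whose size is uncertain. At equal true rates the longer-treated arm is expected to show more and earlier events. The 2-year combined ratio for higher-risk MDS or AML is about 1.14–1.44 with no off-drug marrows, falls to 1.05–1.11 with one a year and 1.01–1.06 with two, and is smaller at 5 years. These figures depend on assumed time on drug, off-drug marrow frequency and hazards. For AML alone the effect is chiefly a small shift in timing. The primary analysis is untouched. This is an inexpensive improvement to how long-term safety is reported, not a flaw in the trial's main conclusion.

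**What to change.** 1. In Section 9.8, tabulate high/very high IPSS-R progression and AML by arm, separately for on-treatment and post-treatment person-time. Label the split descriptive, because stopping drug is a post-randomization event that depends on response.
2. Accompany any between-arm statement on IPSS-R class progression with a comparison over the common assessed window, through the Day 169 assessment, or through EOT only where EOT is earlier than Day 169. Show it beside full follow-up. Letting the window run to a later EOT would bring the imbalance back.
3. At each long-term contact, record the date and blast result of the most recent routine blood count or marrow, using the record review Section 6.3.2 already permits, so that post-treatment ascertainment can be described.

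**Cost.** Modest extra record abstraction, a small eCRF addition and a few tables; no new procedure and no change to treatment rules. **Limits.** Events in the 24-week window will be few: at the assumed 0.03–0.10 per year, 175 × 24/52 × 0.03 to 0.10 ≈ 2 to 8 true transitions per arm. Subjects stopping before Day 169 contribute less assessed time. Recording routine tests describes off-drug ascertainment but does not equalise it.
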